Our **hypotheses** are the following:

Hypothesis 1: ACTH gel is superior to no treatment in maintaining remission in children with frequently relapsing or steroid dependent nephrotic syndrome.

Hypothesis 2: Relapses in children with frequently relapsing or steroid dependent nephrotic syndrome receiving ACTH gel will increase when the dose of ACTH gel is reduced by 50%.

Hypothesis 3: ACTH gel will increase the percentage of children with frequently relapsing or steroid dependent nephrotic syndrome that remain relapse free off medication.

Primary end-points:

The primary end-point related to Hypothesis 1 is the proportion of patients in each arm with a relapse during the initial 6 months of treatment.

The primary end-point related to Hypothesis 2 is the proportion of relapse-free patients during the first 6 months and second 6 months of treatment with ACTH. This will include patients initially randomized to ACTH and patients who receive ACTH as rescue therapy following their initial relapse in patients randomized to no treatment.

The primary end-point related to Hypothesis 3 is the proportion of patients who have relapses in the 6 months following completion of one year of ACTH. This will be compared to the

proportion of patients with relapses during the initial 6 months in the patients randomized to no treatment.

Secondary end-points:

Our secondary end-points are the following:

1. The total prednisone exposure over the initial 12 months in the two groups.
2. The number of relapses over the initial 6 months in the two groups.
3. The change in BMI, height SDS, and cholesterol over the study period for both groups

Study Design and Methods

The experimental design is a multi-center, prospective, controlled open label, randomized trial comparing ACTH gel and no treatment in preventing relapses in pediatric patients with frequently relapsing or steroid dependent nephrotic syndrome.

Patients will be randomized in a 1:1 ratio to either no treatment or treatment with ACTH gel. The primary outcome will be the presence of a relapse within 6 months of starting ACTH gel or no treatment.

After initial recruitment, enrollment will begin with a screening visit to determine eligibility and obtain informed consent and assent. Randomization and weaning of all other medications for the treatment of NS will begin after remission has been achieved for those with active relapse. There will be a 2 week overlap of ACTH and current immunosuppressive medications:

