1. ACTH will be initiated 2 weeks prior to the completion of the prednisone taper for patients who are receiving prednisone at the time of consent.
2. ACTH will be initiated 2 weeks prior to stopping preventive medications such as tacrolimus, cyclosporin, and mycophenolate.

Patients randomized to no treatment will be followed for up to 6 months or until disease relapse, whichever occurs first. Patients who relapse within 6 months will be given the option of reassignment to the ACTH treatment group after remission has been achieved using conventional corticosteroid therapy.

Patients randomized to ACTH treatment will be given ACTH for 12 months. During the second 6 months, the ACTH dose will be reduced to 50% of the starting dose. The outcome of interest is the presence of relapses after dose reduction. Follow-up will occur throughout the 12 months of therapy, and also for 6 months following the completion of ACTH therapy. The outcome of interest is the percentage of patients with relapses in the 6 months after completing a 12 month course of ACTH treatment.

Visits

Screening visit: The study will be explained to the patient and family. Inclusion and exclusion criteria will be reviewed to determine eligibility. Consent and assent will be obtained as appropriate. Medical history will be recorded. A physical exam will be performed. If indicated, a

plan for prednisone tapering will be explained to the family. The date of the baseline visit will either be determined at that visit or via telephone for patients who are currently in relapse.

Baseline visit: The patient will be seen and have baseline labs (renal function panel, cholesterol, urinalysis, urine protein/creatinine ratio). A urine pregnancy test will be performed in females of childbearing age (achieved menarche) who are randomized to ACTH treatment along with counseling in required birth control. An interval medical history and quality of life (QOL) survey will be performed. Patients will have a physical examination. Patients will be randomized to either ACTH gel or no treatment. Patients will be given Albutix and instructions for daily monitoring of the urine and recording the results. Patients randomized to ACTH gel will receive their first injection in clinic and be taught how to perform injections at home. A stop date for other immunosuppressive medications will be provided, if appropriate, 2 weeks after starting ACTH.

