Follow-up visits in patients randomized to ACTH will occur 1 month, 2 months, 4 months, 6 months, 8 months, 10 months, 12 months, 15 months and 18 months after the baseline visit. An interval medical history (including screening for adverse events) will be performed. Patients will have a physical examination. A renal function panel, cholesterol, urinalysis, urine protein/creatinine ratio, and QOL survey will be obtained at months 6 and 12. Urine pregnancy test, if applicable, will be obtained at months 4 and 8.

[figure not shown]
The dose of ACTH will be reduced by 50% after 6 months of treatment. Patients who have significant side effects attributed to ACTH will have an earlier dose reduction (i.e., before 6 months) at the discretion of each individual site PI. The PI will be asked to review possible side effects with the patient at each visit and decide if a dose reduction is warranted. A telephone contact will be made 1 month after dose reduction to screen for symptoms of adrenal insufficiency.

Relapses will be treated with prednisone, at 2mg/kg/day or 60mg/m²/day (maximum dose 60 mg) until remission is achieved, with a subsequent taper off therapy over 4 weeks. For patients receiving a reduced dose of ACTH, the dose will be reverted back to the last effective dosage on which remission was sustained, and continue at that dose until the end of the study. If >1 relapse occurs on the initial ACTH dose, ACTH therapy will be considered a failure and terminated.

The total ACTH therapy duration will be 12 months, after which, the subjects will be seen at follow-up at 15 and 18 months.

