Patients who are randomized to no treatment will have follow-up visits up to the time of relapse, at 1 month, 2 months, 4 months, and 6 months. An interval medical history (including screening for adverse events) will be performed. Patients will have a physical examination. A renal function panel, cholesterol, urinalysis, and urine protein/creatinine ratio, and QOL survey will be obtained at month 6. They will be treated with prednisone for any relapses and have the option to be placed on ACTH during the last 2 weeks of the prednisone taper if the relapse occurred within 6 months of the baseline visit. The subsequent visit schedule and procedures will be identical to the schedule for subjects initially randomized to ACTH (i.e., it will include a baseline visit, telephone contacts, and 18 months of follow-up). Alternatively, the patient may elect to be treated via standard of care in collaboration with the treating nephrologist, and the patient will then exit the study.

Flow Chart of Study Course

Participant Selection

Sixty subjects will be recruited from 10-12 large pediatric centers. Subjects may also be identified via physician or self-referral from advertisements placed on NephCure. Additionally, subjects may be recruited from registries of individuals interested in research participation.

Patients and their caregivers will be approached during a relapse of nephrotic syndrome or within 4 months of a relapse. The following criteria will be reviewed during the screening visit to determine eligibility:

Inclusion criteria

1. Age >1 year at onset of nephrotic syndrome
2. Age 2-20 years at time of randomization
3. Estimated GFR > 50 ml/min/1.73 m² at most recent measure prior to randomization (Schwartz formula)
4. Steroid responsive nephrotic syndrome throughout clinical course (never required a second agent to attain remission of a relapse of nephrotic syndrome)
5. History of frequently relapsing or steroid dependent nephrotic syndrome (defined as 2 or more relapses within 6 months after initial therapy or 4 or more relapses in any 12 month period OR relapse during taper or within 2 weeks of discontinuing prednisone).
6. Patient is currently in relapse of nephrotic syndrome or had a relapse within the last 4 months (defined as an increase in the first morning urine protein to creatinine ratio ≥ 2 or Albustix reading of ≥ 2 for 3 or 5 consecutive days).

Exclusion criteria

1. Prior treatment with ACTH.

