Using the method of Lan-DeMets, we list the boundary p-value for this sequential design. Thus, after our first interim look, we will reject the null hypothesis of equal 6 month relapse rates between ACTH gel and no treatment if our test statistic renders a p-value $< .006$. According to the intent to treat principle, patients will be analyzed according to the treatment they have been assigned to during the randomization procedure. The odds ratio of ACTH versus no ACTH, plus the Wald 95% confidence interval, will be also be calculated.

The primary end-point related to specific aim 2 is the proportion of relapse-free patients during the first 6 months and second 6 months of treatment with ACTH. This will include patients initially randomized to ACTH and patients who receive ACTH as rescue therapy following their initial relapse. We will estimate 6 month and 12 month relapse-free rate using the method of Kaplan-Meier and compare treatments using a log-rank test.

The primary end-point related to specific aim 3 is the proportion of patients who have relapses in the 6 months following completion of one year of ACTH. This will be compared to the proportion of patients with relapses during the initial 6 months in the patients randomized to no treatment using a z test statistic. Odds ratios of ACTH vs no ACTH will also be calculated.

We will also compare patients as randomized by secondary endpoints such as total prednisone exposure in 12 months, number of relapses, cholesterol and change in BMI with two sample t-tests. If normality assumptions do not hold, appropriate non-parametric methods will be used.

Growth data collected during the study will be summarized descriptively for each treatment group at each time point. Based on height data collected during the study and published reference height information, the height standard deviation score (SDS, also called z-score) will be computed for each patient at each time point as:

$$(\text{Height} - \text{mean height for that age category}) / \text{SD of height for that age category}.$$

Descriptive statistics of this endpoint will be presented by time point and the z-scores will allow identification of potential outliers.

Treatment Assignment and Randomization

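### Cholesterol and change in BMI are compared by t-tests without a baseline covariate, and the cholesterol test is not worded like its end-point; a month-6 ANCOVA would be more precise at almost no cost

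*Combined protocol and SAP*

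**What the plan says.** - **End-point.** Under Secondary end-points, the third item is "The change in BMI, height SDS, and cholesterol over the study period for both groups". All three measures are changes, and no time point is given.
- **Test.** The Statistical Analysis section compares patients as randomised on "cholesterol and change in BMI with two sample t-tests". BMI is written as a change and cholesterol is not. The fallback is "If normality assumptions do not hold, appropriate non-parametric methods will be used". No baseline covariate appears anywhere in the plan.
- **Height SDS.** The same section plans descriptive statistics by time point for this measure, and names no between-arm test.
- **Baseline data.** At the baseline visit patients have "baseline labs (renal function panel, cholesterol, urinalysis, urine protein/creatinine ratio", among other procedures. Height and weight are not listed by name, but that visit includes a physical examination, and a change in BMI cannot be computed without a baseline BMI.
- **Follow-up data.** In the ACTH arm, the set of tests that includes cholesterol and the "QOL survey will be obtained at months 6 and 12" (Interval Visits). Patients randomised to no treatment "will have follow-up visits up to the time of relapse, at 1 month, 2 months, 4 months, and 6 months", with cholesterol at month 6 only.

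**The concern.** Cholesterol and BMI are among the measures on which the Introduction bases its case for ACTH: an improved lipid profile, and less of the weight gain seen with corticosteroids. The trial plans 30 patients per arm and states no power for these comparisons, so precision is scarce.

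A t-test on final values makes no use of baseline. A t-test on change subtracts the whole baseline, which over-corrects when the correlation between baseline and follow-up is below 1. ANCOVA estimates how much of the baseline to take out. In a randomised comparison with equal arms it is, in large samples, at least as precise as either t-test, and it also removes the effect of a chance baseline imbalance.

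The missing word before cholesterol adds a second problem. Two analysts could follow the plan faithfully and run different tests.

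**Working it through.** **The plan's own figure.** The plan gives no power, standard deviation or correlation for cholesterol or BMI. Its only power figure, 91%, belongs to the relapse end-point (70% against 30%, 30 per arm, two looks). It reproduces closely: 0.893 for a fixed design with pooled variance, and 0.897 to 0.917 for the two-look design, depending on method. It says nothing about the secondary end-points.

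**Inputs.** 30 per arm and 1:1 allocation come from the plan. Assumed: equal SDs at baseline and follow-up, a linear relation, complete data, and r over a range.

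**Formulas.** Variance per patient, in units of SD²:

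- final-value t-test: 1
- change-score t-test: 2(1 − r)
- ANCOVA: 1 − r²

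So ANCOVA/final = 1 − r², and ANCOVA/change = (1 − r²) / [2(1 − r)] = (1 + r)/2. Standard-error (SE) ratios are the square roots.

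| r (assumed) | Change-score variance | ANCOVA variance | ANCOVA/final: variance (SE) | ANCOVA/change: variance (SE) |
|---|---|---|---|---|
| 0.3 | 1.40 | 0.91 | 0.91 (0.954) | 0.65 (0.806) |
| 0.5 | 1.00 | 0.75 | 0.75 (0.866) | 0.75 (0.866) |
| 0.7 | 0.60 | 0.51 | 0.51 (0.714) | 0.85 (0.922) |
| 0.8 | 0.40 | 0.36 | 0.36 (0.600) | 0.90 (0.949) |
| 0.9 | 0.20 | 0.19 | 0.19 (0.436) | 0.95 (0.975) |
| 0.95 | 0.10 | 0.0975 | 0.0975 (0.312) | 0.975 (0.987) |

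**Cholesterol read as a raw value.** The 95% half-width of the final-value comparison is 1.96 × √(2/30) = 0.506 SD. ANCOVA gives 0.438, 0.361 and 0.304 SD at r = 0.5, 0.7 and 0.8.

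**Cholesterol read as a change.** The change-score half-width is 0.506, 0.392 and 0.320 SD at the same r, against the same ANCOVA values. At r = 0.5, ANCOVA with 30 per arm is as precise as either t-test with 30/0.75 = 40 per arm.

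**BMI, tested as a change.** If r is 0.8 to 0.95, the SE ratio is 0.949 to 0.987, a fall of about 5% to 1%.

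**Small-sample cost.** Estimating the slope with 60 patients multiplies the ANCOVA variance by about 57/56. ANCOVA then still beats the final-value test when r² > 1/57 (r above about 0.13), and the change-score test when r < 2 × 56/57 − 1 = 55/57 (r below about 0.96).

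**Chance imbalance.** The baseline difference between arms has an SE of √(2/30) = 0.258 SD, so a difference above 0.25 SD in either direction occurs about one time in three. At r = 0.7, such an imbalance shifts a final-value difference by 0.7 × 0.25 = 0.175 SD. It shifts a change-score difference by (1 − 0.7) × 0.25 = 0.075 SD the other way. ANCOVA removes both shifts.

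**The complete-data assumption.** At the plan's assumed 70% control relapse rate, 30 × 0.30 = 9 controls reach month 6 relapse-free. If only those 9 have a month-6 value, against 30 on ACTH, the SE factor is √(1/30 + 1/9) = 0.380 instead of 0.258, about 47% larger.

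**The case against.** A reader might infer that the planned tests ignore baseline altogether. The documents do not support that. BMI is tested as a change, so its baseline enters by subtraction and chance imbalance is partly handled. For cholesterol, the analysis sentence is a shorthand list, and the missing word may be a slip. The 49% and 64% reductions therefore rest on a reading that the end-point list contradicts. This objection stands, and it limits the point.

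It can also be said that a t-test in a randomised comparison is valid, that these are unpowered secondary end-points, and that this is a preference for efficiency. With complete data the first two are true. But r is unknown, and each t-test does badly somewhere: the final-value test at high r and the change score at low r. ANCOVA avoids having to guess, using data already collected.

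The most serious objection is control follow-up. Controls who relapse either restart the schedule on ACTH with a new baseline visit or leave the study, so month-6 values may be missing, and missing because of relapse. That loss may exceed anything gained by adjustment, and it makes the comparison selective. With about 30 against 9 and unequal slopes, plain ANCOVA is not even guaranteed to beat a t-test. All of this stands. It shows that baseline adjustment is not a cure for missing control data, but it does not make the unadjusted test the better choice.

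Finally, height SDS has no planned t-test, so there is nothing to replace for that measure.

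**Conclusion.** The point holds as a modest, inexpensive improvement together with one wording conflict that needs correcting. The plan specifies no baseline adjustment for cholesterol or BMI, and its two statements about cholesterol disagree.

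Against change-score tests the variance gain is 25%, 15% and 10% at r = 0.5, 0.7 and 0.8. For BMI it is probably at the small end, about 1 to 5% of the standard error if r is 0.8 to 0.95. Only if cholesterol is tested as a raw value do the larger gains of 25%, 49% and 64% apply. The case therefore rests mainly on cholesterol.

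These figures assume a value for r, equal SDs, linearity and about 30 patients per arm with data. The last assumption is doubtful for controls. The benefit is precision and correction of chance imbalance on secondary end-points. Nothing here suggests an inflated type I error or touches the primary analysis.

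**What to change.** In the Statistical Analysis section, replace the t-tests for cholesterol and BMI with this: the arms are compared as randomised by ANCOVA of the month-6 value on treatment, with the patient's own value at the randomisation baseline visit as covariate. Month 6, counted from randomisation, is the last visit with scheduled labs in both arms. Keep a t-test or a rank-based test as a named sensitivity analysis.

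Use the same description of the cholesterol measure, and the same time point, in Secondary end-points and in Statistical Analysis. Month 6 narrows the end-point's present reference to the whole study period, so the change should be stated openly.

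Leave height SDS descriptive, or add a between-arm ANCOVA for it and label it as an addition.

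Report how many patients in each arm contribute a month-6 value, and say that missing control values after relapse are a separate problem that this model does not solve.

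The cost is two or three sentences and one degree of freedom. The analysis needs no visit or measurement beyond those planned; listing height and weight by name at the baseline and month-6 visits would remove any doubt about BMI.

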ACTH for Frequently Relapsing and Steroid Dependent Nephrotic Syndrome

Principal Investigator (IND Holder): [name], Ph. D.

Unique Protocol ID: IRB00068101

NCT02132195

Date: March 5, 2014

ACTH for Frequently Relapsing and Steroid Dependent Nephrotic Syndrome

INVESTIGATORS: [name]., [name], Ph.D.

Sponsor (IND Holder): [name], Ph. D.

Study-Supporter: Questcor Pharmaceuticals, Inc.

Abstract

ACTH, given in the form of a long-acting, repository injection, has recently been shown to be effective in inducing disease remission in adult patients with nephrotic syndrome. Side effects are decreased compared to corticosteroids and other immunosuppressive agents, making it an attractive therapeutic choice for patients with frequently relapsing and steroid dependent nephrotic syndrome (FRNS and SDNS). No published data exist on the use of long-acting ACTH gel in the pediatric nephrotic population. We propose a multi-center, prospective, controlled open label, randomized trial to evaluate the effects of ACTH on the symptoms and biochemical profile in children with FRNS and SDNS.

Introduction

Treatment of frequently relapsing and steroid dependent nephrotic syndrome (FRNS and SRNS) in children remains challenging. Current treatment exposes patients to morbidity from prolonged, high-dose corticosteroids as well as various immunosuppressive agents that have a variety of serious side effects, including nephrotoxicity¹. Chronic corticosteroid exposure leads to growth retardation, obesity, decreased bone density, and other complications. Short-term use of corticosteroids is associated with behavioral changes. Furthermore, relapses of nephrotic syndrome are associated with potential complications such as infection and thromboembolic disease^{2,3}.

During the 1950s, parenteral adrenocorticotrophic hormone (ACTH) was an effective treatment for nephrotic syndrome. ACTH was utilized in frequent, often four times daily, high dose injections for days to weeks, necessitating hospitalization for treatment and monitoring⁴⁻⁷. Oral prednisone ultimately replaced ACTH.

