2. Cyclophosphamide or rituximab within the last 4 months.
3. Lactation, pregnancy, or refusal of birth control (abstinence qualifies) in females with child-bearing potential.
4. Planned treatment with live or live-attenuated vaccines once enrolled in the study.
5. Participation in another therapeutic trial concurrently or 30 days prior to randomization.
6. Active/serious infection (including, but not limited to Hepatitis B or C, HIV).
7. Malignancy concurrently or within the last 2 years.
8. Systolic or diastolic blood pressure >95% for age/height while receiving maximal doses of 3 or more medications.
9. Prior diagnosis of diabetes mellitus (Type I or II) or fasting glucose >200mg/dL
10. Organ transplantation
11. Contraindications to Acthar: scleroderma, osteoporosis, systemic fungal infections, ocular herpes simplex, recent surgery, history of or the presence of peptic ulcer, congestive heart failure, uncontrolled hypertension, primary adrenocortical insufficiency, or adrenal cortical hyperfunction
12. Secondary cause of nephrotic syndrome (e.g., SLE)
13. Biopsy demonstrating a diagnosis other than minimal change, FSGS or a variant (mesangial proliferation, IgM nephropathy)
14. Inability to consent/assent

Statistical Analysis

The primary end-point of the study and on which the statistical power is based is the proportion of patients who have a relapse in the 6 months following randomization to either ACTH or no ACTH.

We hypothesize that the 6 month relapse rate for patients receiving no treatment is 70%. In order to detect a 6 month relapse rate of 30% for patients receiving the ACTH gel, we will randomize 30 patients in each arm using a two sided z test with $\alpha=.05$. Our statistical power to detect such a difference is 91% which assumes two interim analyses at 50% and 100% of accumulated information. That is, once 30 patients have 6 month relapse data, we will conduct the first interim analysis. The last one will be completed once we have relapse data on all 60 patients. The table below gives the operating characteristics for such a design:

| Number of Patients with 6 Months Data | Boundary p-value |
|--|-------------------------|
| 30 | 0.006 |
| 60 | 0.045 |

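### Change in height SDS is a named secondary end-point, but the growth paragraph plans only descriptive SDS levels, so the plan need not yield an estimate or interval for it

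*Combined protocol and SAP*

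**What the plan says.** The third item under Secondary end-points reads: "The change in BMI, height SDS, and cholesterol over the study period for both groups".

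The Statistical Analysis section handles the three parts of that item differently. Arms are compared as randomised on "secondary endpoints such as total prednisone exposure in 12 months, number of relapses, cholesterol and change in BMI with two sample t-tests", with non-parametric methods if normality fails. BMI and cholesterol are in that list and height is not.

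Height has its own paragraph: "Growth data collected during the study will be summarized descriptively for each treatment group at each time point". The SDS "will be computed for each patient at each time point as" height minus the reference mean, divided by the reference SD. The planned output is: "Descriptive statistics of this endpoint will be presented by time point and the z-scores will allow identification of potential outliers".

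Nothing there defines a change from baseline, a contrast between arms or a confidence interval. Nor does it say in which group a control who later takes ACTH is counted, or which of that child's two baseline visits applies.

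**The concern.** The end-point is a change within a child. The planned output is a set of group means of levels. If the growth paragraph is taken as the whole plan for height, the report can satisfy it without giving the named end-point or any measure of its uncertainty.

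A reader would want that result. The Introduction says: "Chronic corticosteroid exposure leads to growth retardation, obesity, decreased bone density, and other complications". It also calls children especially vulnerable to the effects of steroids on growth, and notes that ACTH acts partly by raising endogenous steroid production. Height SDS is the only measure of growth in height among the end-points.

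Level tables are a weak substitute for two reasons. They carry the full spread of height between children, which most of the change analysis removes. And the children behind each mean differ from one time point to the next, because control follow-up stops at relapse or month 6 and some children exit.

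**Working it through.** **The plan's own figure.** The plan gives no precision or power for height SDS. Its 91% power is for the primary relapse comparison and has no bearing here.

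**Inputs from the documents**
- Arm size (Statistical Analysis): "we will randomize 30 patients in each arm".
- Six-month relapse rate without treatment: 70% (Statistical Analysis).
- Control follow-up ends at relapse or month 6. A control who relapses within 6 months may move to ACTH, on a new 18-month schedule, or choose standard care and exit (Study Design and Methods; Interval Visits).
- ACTH children are followed to month 18, but exit for intolerance despite an early dose reduction, or after two relapses on the highest tolerated dose (ACTH Treatment; Interval Visits).

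**Assumptions, none of them in the documents**
- SD of height SDS: 1.0.
- Correlation ρ between a child's baseline and later SDS: 0.90, 0.95 or 0.98.
- Yardstick difference: 0.25 SDS, chosen only to give scale.

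**Step 1: who is left.** 30 × 0.70 = 21 controls reach the end of control follow-up by relapse within 6 months, and 30 − 21 = 9 remain relapse-free. No untreated follow-up is scheduled after month 6, so month 6 is the last scheduled time point common to both arms.

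**Step 2: effect of membership on a mean level.** If the 9 were a random subset of the 30, the mean SDS would move from the first set to the second with standard error √(1/9 − 1/30) = √0.0778 = 0.28, with no child growing differently. They are not random, because they are selected on relapse, so selection may be added to this noise.

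**Step 3: precision of a between-arm difference.**
- Levels: SE = SD × √(1/n₁ + 1/n₂).
- Change: SE = SD × √(2(1 − ρ)) × √(1/n₁ + 1/n₂).

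With 30 per arm, √(2/30) = 0.258. With 30 versus 9, √(1/30 + 1/9) = 0.380. The factor √(2(1 − ρ)) is 0.45, 0.32 and 0.20.

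| Comparison | SE, 30 v 30 | 95% half-width | SE, 30 v 9 | 95% half-width |
|---|---|---|---|---|
| Levels | 0.26 | 0.51 | 0.38 | 0.74 |
| Change, ρ = 0.90 | 0.12 | 0.23 | 0.17 | 0.33 |
| Change, ρ = 0.95 | 0.08 | 0.16 | 0.12 | 0.24 |
| Change, ρ = 0.98 | 0.05 | 0.10 | 0.08 | 0.15 |

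For the 0.25 SDS yardstick at two-sided 5%, power on change is 58%, 86% and over 99% with 30 per arm, and about 31%, 55% and 91% with 30 versus 9. The same calculation on levels gives 16% and about 10%.

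**Step 4: sensitivity.** Adjusting for baseline, with SE = SD × √(1 − ρ²) × √(2/n), gives 0.11, 0.08 and 0.05 with 30 per arm, much the same as change. At ρ = 0.80 the SE for change is 0.16, still below 0.26. A larger SD scales every SE alike: at SD 1.2, levels give 0.31 and change 0.14, 0.10 and 0.06. Change is more precise than level whenever ρ exceeds 0.5.

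**The case against.** The t-test sentence introduces its list with such as, and the list is governed by secondary end-points, of which change in height SDS is one. A reader might infer that a comparison of height is ruled out. The documents do not support that. What stands is that the only paragraph written for height plans levels, so the comparison is neither excluded nor promised.

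A reader might also infer that the plan would mask or bias away a growth effect of ACTH. That goes too far. With complete follow-up as randomised, spread between children costs precision and does not bias the contrast. With the same children at both times, the difference of mean levels is the mean change, so the tables would then lack only its precision. No test of levels is planned, so the 16% is a yardstick and not the power of a planned analysis. The SD, the correlations and the 0.25 SDS have no source in the documents, and an SD near 1 describes a reference population, not necessarily these patients.

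Nor is height SDS declared the trial's main measure of growth harm. None of the three hypotheses concerns growth, and the Introduction presents ACTH as a way to spare children steroid effects. Descriptive reporting is defensible in 60 patients with no untreated follow-up scheduled after month 6.

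Finally, analysing change does not cure the membership problem. Restricted to controls still relapse-free at month 6, it would compare a group selected after randomisation. Relapsed controls do not all leave the study: those who take ACTH are followed further and can be kept in their randomised arm. These points limit the claim and shape the remedy. They do not supply the missing estimate.

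**Conclusion.** The mismatch is in the text. The end-point is a change in both groups, the growth paragraph delivers only levels by time point, and the plan as written need not report an estimate or interval for it.

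On the assumed SD of 1 and correlation of 0.90 to 0.98, a contrast of change has a standard error between about one fifth and just under half that of a contrast of levels. The ordering needs only a correlation above 0.5. The count of about 9 relapse-free controls rests on the plan's own 70% rate.

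The documents do not show that a growth effect would be hidden, or that ACTH is expected to impair growth. The point is worth correcting because the better analysis is cheap. It concerns the analysis wording of one secondary end-point and leaves the primary analysis and clinical management untouched.

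**What to change.** In the growth paragraph of the Statistical Analysis section:

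1. Define each child's change in height SDS from that child's own randomisation baseline.
2. Report the as-randomised difference in change at month 6, adjusted for baseline SDS, with a 95% interval. Keep relapsed and crossed-over controls in their randomised arm, using their available height nearest month 6.
3. Use all post-baseline heights, for example in a mixed model, so that children who exit early still contribute. Report how many in each arm lack a height.
4. Separately, report the mean within-child change from ACTH start to months 6 and 12 with 95% intervals, for all children given ACTH. Label it as uncontrolled and as including the effect of prednisone given for relapses.
5. Keep the SDS levels by time point as a listing.

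The cost is analysis wording and a few lines of code. The section already relies on height data collected during the study, and no visit, dose or clinical rule changes. There are two downsides to state in the report. The month-6 contrast is a treatment-policy comparison that includes rescue prednisone and ACTH in controls, so it does not isolate ACTH against no treatment. And the loss of children who exit may be informative, which a mixed model does not fully repair.
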